### 8.2. POWER ANALYSIS

*For each confirmatory outcome, please provide power analyses demonstrating proposed sample sizes will be able to detect expected effect sizes for the outcomes targeted. Refer to previous studies of similar interventions for estimates of the required sample to inform power analyses. Note: If an impact evaluation is not proposed, this issue does not need to be addressed. You may use the table below to report the assumptions used in your power calculations, as well as the resulting minimum detectable impact for your confirmatory outcomes or provide them in the space below.*

Though not an RCT, the Power Analysis is as follows:

	Outcome 1:	Outcome 2:	Outcome 3:
Outcome Name	Parenting Attitudes	Father Relationship Behavior (parenting/co-parenting)	Father Financial Behavior
Continuous or binary?	Continuous	Continuous	Continuous

Level of significance (e.g., 0.05 percent)	0.05	0.05	0.05
Number of sides of test (one- or two-tailed)	2 tailed	2-tailed	2-tailed
Power (e.g., 80 percent)	80%	80%	80%
Total number of individuals in analytic sample	483	483	483
If continuous outcome, enter the standard deviation of the outcome (>0)	nFORM	nFORM	nFORM
Proportion of individual-level (or within-group) variance explained by covariates	nFORM	nFORM	nFORM
Minimum detectable effect size	0.030	0.030	0.030

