### 8.3. METHODS TO PROMOTE SUFFICIENT PROGRAM PARTICIPATION

*Please describe methods to promote sufficient program participation in the table below.*

What methods will you use to ensure sufficient sample is recruited, enrolls, and participates in the program?	Action for Children will over-recruit to ensure sufficient sample size. Incentives will be offered at various times in the curriculum to keep participants active.
Who will be responsible for recruiting the evaluation sample?	Applicants will be enrolled via street outreach or referral. Action for Children will use multiple targeted marketing platforms-such as billboards, radio, print, social media, flyers, brochures, and posters. Action for Children will also have an experienced and trained full-time recruiter, part-time recruiter, and other staff to assist in recruitment.

**Please describe any incentives to be offered for program participation and/or completion and/or data collection and/or participation in the evaluation.**

Participants will be incentivized throughout participation in primary workshops as well for completing the one-year follow-up survey for evaluation purposes.

- \$25 gift card after completing Enrollment Surveys and attending 3 sessions
- \$25 gift card after the completion of Session 6
- \$75 gift card after the completion of Session 11 or 12 and the nFORM Post-Program Survey (& OLLE Post-Survey-only during evaluation enrollment period: ended 4/12/2024) if attendance is at least 90% for the core curriculum workshops

A \$50 gift card will be given for completion of the 1 Year Follow-Up Survey for evaluation purposes.

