#### 9.4. ENSURING AND MONITORING DATA COLLECTION

*Describe plans for training data collectors and for updating or retraining data collectors about procedures. Detail plans to regularly review data that have been submitted and to assess and swiftly address problems.*

This evaluation will utilize both post-program surveys (completed at the completion of core programming) and follow-up surveys collected one year after enrollment / baseline. The methods for these data collections differ. The primary driver for post-program survey completion is high rates of program retention. This data point will be collected during the last workshop session – after (but during the same session of) the completion of the nFORM post-program data collection. As such only those individuals who complete the program and who are at the data collection session will participate in the post-program data collection.

All program staff and evaluation staff will undergo a rigorous set of trainings to prepare for the evaluation. All staff receive an overview and introductory training to present the goals and objectives of the evaluation effort and its importance to the overall project. Next all staff receive training on human subject's protection and are required to pass a certification test on the subject matter. All staff will also receive a detailed training on the details of the evaluation including the evaluation tools, timing and data collection process.

In addition, the Data Manager and the primary local evaluation staff will undergo a rigorous training process to better understand the context of HMRF research, training on data collection procedures they will be responsible for, and training on the nFORM system and use of nFORM data in a CQI process. MER is creating networks of CQI Data Managers and Evaluation Project Managers across the 12 projects that we are evaluating so that all staff have access to experienced Data Managers and evaluation staff who have done this work previously. This training takes the form of weekly training sessions that are currently under way.

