Missing data for the implementation outcomes could happen as a result of programmatic data entry issues. For the sake of this evaluation, we assume that any primary or support services received by a participant are being accurately logged into nFORM, so a lack of documented attendance, service contacts, referrals, etc. is indicative of lack of services (i.e., a participant not receiving the program components as intended).

Assessing non-response bias

We will conduct response rate analysis for each primary outcome of interest to assess non-response bias and adjust for threats to internal validity. Using data from the Applicant Characteristics Survey, we will look at demographics (race, ethnicity, age, education level) and primary reason for joining the program among participants who fall into each of the following categories: 1) non-respondents who answered no surveys after the ACS, 2) respondents who completed the pre-survey only, 3) respondents who completed the post-survey only, and 4) respondents who completed both the pre- and post-survey (complete case).

Analytic approach

The main goal of this descriptive study is to assess pre-post change scores in the attitudinal outcomes listed above and assess pre-to-one-year follow-up change scores in the behavioral outcomes listed above among program participants before and after primary workshops. We will use paired sample t-tests to assess the magnitude and significance of changes among program participants in the analytic sample for each outcome. For binary economic stability outcomes, we will descriptively report the percent of participants who opened a checking or savings account one year after enrollment, compared to the percent who had opened these accounts before the program. We will adjust our p-values for multiple hypothesis testing and report the adjusted p-values in the appendix of the final report.

2. Data Archiving and Transfer

Briefly describe the planned approach data arching and transfer by addressing questions below.

What procedures and parameters are established for all aspects of data/information collection necessary to support archiving data collected as part of the evaluation?

Examples include informed consent, data maintenance, de-identifying data procedures.

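### The paired t-tests assume independent change scores although services are delivered in facilitator-led workshops, so standard errors may be too small, most plausibly for parenting attitudes (R4)

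*SAP*

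**What the plan says.** SAP section 1, under Analytic approach, sets the test: "We will use paired sample t-tests". It applies to pre-post change in the attitudinal outcome and to change from baseline to one year in the behavioural outcomes. The checking and savings account items are instead to be reported as percentages. P-values are to be adjusted for multiple testing, by a method that is not named.

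The unit of analysis is the individual father (Protocol 8.1 and the note to the logic model). The SAP's dosage model lists attendance hours and father-level covariates, with no term for workshop or facilitator. The power table in Protocol 8.2 has no entry for cluster size, ICC or design effect.

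On delivery, Protocol 8.3 ties incentives to numbered sessions and to whether "attendance is at least 90% for the core curriculum workshops". Protocol 9.2 has a workshop facilitator run orientation. On the exit survey, Protocol 9.4 says: "This data point will be collected during the last workshop session". Protocol 9.3 has a case manager or facilitator proctor the surveys and help where needed. The one-year survey differs: Protocol 9.5 describes tracking by mail and email, followed by completion online or by phone with evaluator staff.

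**The concern.** Pairing removes the correlation between two measurements on the same father. It does nothing about correlation of change between fathers who attend the same workshop series. Such fathers may share a facilitator, peers and a calendar period. For R4 they may also share the session at which the outcome is recorded.

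Delivery may also vary over time. Study enrollment runs for three years (Protocol, Evaluation Enrollment), and the quality-improvement process is meant to keep adjusting implementation as data come in (Protocol 9.4). Fathers taught at different times may therefore receive somewhat different services. Stable differences between groups cancel in a change score, but differences in how much groups change do not.

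R1, R2 and R4 are all labelled confirmatory in Protocol 1.2, and publication is planned. If change is positively correlated within series, the paired t-test gives intervals that are too narrow and rejects too often. The multiplicity adjustment does not repair this, because it takes the uncorrected p-values as its input.

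**Working it through.** **Inputs from the documents (Protocol 8.2).** "Total number of individuals in analytic sample": 483 for each outcome; two-tailed alpha 0.05; power 80%; stated minimum detectable effect 0.030.

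**The plan's own figure.** For a paired test the detectable effect in SD units of change is (1.960 + 0.842)/√n, with the numerator 2.8016 before rounding. At n = 483 this is 2.8016/21.977 = 0.127 (0.128 by the noncentral t). The stated 0.030 is not reproduced; it would need about (2.8016/0.030)² ≈ 8,721 fathers. That mismatch is a separate problem and clustering does not explain it. The comparison below starts from 0.127.

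**Inputs that are assumed.** The documents give neither the number of fathers per workshop series (m) nor the ICC of the change score. I take m = 8 to 15 analysed fathers and ICC = 0.01 to 0.05.

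**Formulas.**
- Design effect: DE = 1 + (m − 1) × ICC.
- True SE / reported SE = √DE; shortfall of the reported SE = 1 − 1/√DE.
- True size of a nominal two-sided 5% test = 2 × [1 − Φ(1.96/√DE)].
- Detectable effect = 2.8016 × √(DE/483).

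| m | ICC | DE | True / reported SE | Reported SE too small by | True size | Detectable effect (SD) |
|---|---|---|---|---|---|---|
| any | 0 | 1.00 | 1.000 | 0% | 5.0% | 0.127 |
| 8 | 0.01 | 1.07 | 1.034 | 3% | 5.8% | 0.132 |
| 8 | 0.05 | 1.35 | 1.162 | 14% | 9.2% | 0.148 |
| 12 | 0.01 | 1.11 | 1.054 | 5% | 6.3% | 0.134 |
| 12 | 0.05 | 1.55 | 1.245 | 20% | 11.5% | 0.159 |
| 15 | 0.01 | 1.14 | 1.068 | 6% | 6.6% | 0.136 |
| 15 | 0.05 | 1.70 | 1.304 | 23% | 13.3% | 0.166 |

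Worked at the upper end: DE = 1 + 14 × 0.05 = 1.70 and √1.70 = 1.304. Then 1.96/1.304 = 1.503, giving a two-sided tail of 13.3%, and 0.127 × 1.304 = 0.166.

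**Sensitivity to the assumptions.** With m = 5 and ICC 0.01, DE is 1.04 and the true size 5.5%. With m = 20 and ICC 0.10, DE is 2.90 and the true size 25.0%. The size of the problem therefore depends almost wholly on two quantities that only the trial's data can supply.

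**Which outcomes are affected.**
- R4 (parenting attitudes): t-tested, with both surveys tied to workshop sessions.
- R1 and R2 (parenting and co-parenting behaviour): t-tested, but the second survey is completed individually about a year after enrollment. Clustering would have to come from shared teaching whose effect on change lasts that long, or from the workshop-linked baseline survey.
- R3 account items: no t-test is planned, so no p-value is affected.

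**The case against.** The strongest reply is that clustering is inferred. No passage states group size, number of series, closed cohorts or one facilitator per series, and the logic model figure that specifies delivery is not available to this review. Part of the service is individual job coaching and case management. Surveys are self-entered on an online platform, and orientation is virtual. At the low end of the assumed range the detectable effect moves only from 0.127 to 0.132. This is also a single-group descriptive study, where the lack of a counterfactual limits interpretation more than a modest error in the SE.

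Most of this stands and limits the claim. Several stronger readings should therefore be set aside:

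- A reader might infer that every confirmatory test is affected. R3 is labelled confirmatory, but the SAP only describes its account items.
- A reader might infer that R4 is measured with fathers together in one room. The documents place the survey at the last session; they do not say that sessions meet in person.
- A reader might take 30% as the shortfall in the reported SE. At DE = 1.70 the true SE is 30% larger, which makes the reported one 23% too small.
- A reader might take 5.8% to 13.3% as the error rate of the reported results. It describes unadjusted 5% tests, and the SAP will also adjust for multiplicity.
- A reader might conclude that the p-values are certainly wrong. With an ICC of zero, nothing changes.

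What the reply does not remove is that independence is assumed without comment, in a programme built around shared sessions, and that it could be checked.

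**Conclusion.** The point holds conditionally. The planned tests assume independent change scores, the delivery described gives good reason to doubt this, and neither document deals with it. If change is positively correlated within a workshop series, standard errors and p-values for the t-tested outcomes are too small. This is most plausible for R4 and less certain for R1 and R2.

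Under the assumed 8 to 15 fathers per series and ICC of 0.01 to 0.05, the consequence runs from minor (true size 5.8%) to material (13.3%). The documents cannot say where in that range the study lies. The point estimates are not in question. This is a worthwhile, low-cost improvement, not a flaw that invalidates the analysis.

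**What to change.** For each t-tested outcome, keep mean change as the estimate. Take its SE, confidence interval and p-value from an intercept-only model of the change score, either with cluster-robust errors by workshop series or with a random intercept for series. Use a small-sample correction for the robust errors: 483 fathers in groups of 8 to 15 would give only about 60 to 32 clusters. Apply the planned multiplicity adjustment to these p-values, and report the ICC for each outcome.

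Use the nFORM workshop attendance record as the cluster identifier. First confirm that it can be exported and linked, because Protocol 12.2 lists the export and linking capabilities of nFORM 2.0 as unknown. State in advance how to classify fathers who attended more than one series, or none; the latter can occur for R1 and R2, since Protocol 9.5 follows up everyone enrolled.

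The cost is a short addition to the SAP, one extra linking step and somewhat wider intervals. With unequal group sizes, the random-intercept version weights fathers slightly differently from the simple mean; the cluster-robust version does not. If the ICC is near zero, the results will barely change, and the report will be able to say so.

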## EVALUATION PLAN

### 1. RESEARCH QUESTIONS

#### 1.1. OVERVIEW OF RESEARCH QUESTIONS

*Please state the research question(s) that the evaluation intends to answer and for each research question indicate the type: implementation or outcome.*

- *Implementation Questions: Identifying whether a program has been successful in attaining desired implementation goals (e.g., reaching intended target population, enrolling intended number of participants, delivering training and services in manner intended, etc.)*
- *Outcome Questions: Identifying whether program is associated with intended outcomes for participants (e.g., do participants' knowledge, attitudes, behaviors, or awareness change?)*

Research questions in this study are framed by a Descriptive Evaluation Design to assess whether outcomes improve for low-income fathers who participate in the All in Dads! (AID!) Project. Primary and secondary outcomes are assessed before and after participants complete core curricula—*Father Factor*, *The New Playbook*, and *Money Smart*—and *Job Readiness Coaching and Career Development* as employment support services (pre to post). Primary outcome measures will indicate whether behavior improved for healthy family relationships (parent, co-parent, and partner). Secondary outcome measures will indicate whether behavior improved for the attitudes and expectations that facilitate and reflect behavior for healthy family relationships and economic stability (financial, employment) (see Table 1 below).

No	Research Question	Implementation or Outcome?
R1	Will participants report significantly healthier parenting behavior one-year after completing primary educational services and employment support services?	Primary Outcome
R2	Will participants report significantly healthier co-parenting behavior one-year after completing primary educational services and employment support services?	Primary Outcome
R3	Will participants report significantly healthier financial behavior one-year after completing primary educational services and employment support services?	Secondary Outcome
R4	Will participants report significantly healthier parenting attitudes after completing primary educational services and employment support services?	Secondary Outcome

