R3	Primary curricula ( Father Factor, The New Playbook, and Money Smart ); Employment Support ( Job Readiness Coaching, Career Development ); Continuous Quality Improvement (CQI) Process	Low-income fathers who are 18+ years with children up to 24 years who are residents of Franklin County in Ohio	Assessment of healthy financial behavior at AID! Project enrollment.	Participants who complete primary and support services will report healthier financial behavior one year after AID! enrollment.	Confirmatory
R4	Primary curricula ( Father Factor, The New Playbook, and Money Smart ); Employment Support ( Job Readiness Coaching, Career Development ); Continuous Quality Improvement (CQI) Process	Low-income fathers who are 18+ years with children up to 24 years who are residents of Franklin County in Ohio	Assessment of healthy parenting attitudes immediately following program completion post-intervention.	Participants who complete primary and support services will report healthier parenting attitudes immediately following program completion..	Confirmatory

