## 9. DATA COLLECTION

### 9.1. CONSTRUCTS AND MEASURES

*Clearly articulate the constructs of interest, measures to evaluate those constructs, and specific data collection instruments. Provide any information on the reliability and validity of the data collection instruments. For standardized instruments, you may provide the citation for the instrument.*

Construct	Measure	Instrument	Reliability and Validity (if standardized instrument, you provide a citation for the instrument)
Parenting Behavior (interaction with children)	1 item: hours spent w/children in last 30 days (interval); 1 item: frequency reach out to children (categories, 5-point scale); 7 items: frequency engage in key behaviors (categories, 5-point scale)	nFORM Community-Based Fathers Survey (A2b, A2c, A5b: b-d, f-i)  *also asked on OLLE; will use data from survey with the most complete data	n/a

Co-Parenting Behavior	11 items: frequency of agreement with key co-parenting behaviors (interval, 5-point scale)	nFORM Community-Based Fathers Survey (A13: a-k)  *also asked on OLLE; will use data from survey with the most complete data	n/a
Father Financial Behavior	2 items: yes or no questions for have resume, checking/savings accounts (dichotomous)	nFORM Community-Based Fathers Survey (B3, B3a)  *also asked on OLLE; will use data from survey with the most complete data	n/a
Parenting Attitudes (toward children)	7 items: frequency of key attitudes (categories, 5-point scale)	nFORM Community-Based Fathers Survey (A3: a-g)  *also asked on OLLE; will use data from survey with the most complete data	n/a

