Primary outcome:				
Parenting Behavior: 1 item	HOURSFU	# hours spent with child		Dosage: hours of attendance per service
	REACHFU	1 = Almost every day to 5 = never in past month	Continuous	

1 item 11 scaled items Co-parenting Behavior: 11 scaled items	ENGAGFU	1 = never to 5 = every day or almost every day	(using nFORM data); Co-variates: development starting points, risk - family structure, demographics, socioeconomic (ACS & OLLE survey data at baseline)
	COPARFU	1 = strongly disagree to 5 = strongly agree	
		1 = yes, 0 = no	

Secondary outcome:

Parenting Attitudes: 7 scaled items Financial Readiness 1 item 1 item	PATTFU	1 = always to 5 = never	Continuous	Dosage: hours of attendance per service (using nFORM data); Co-variates: development starting points, risk - family structure, demographics, socioeconomic (ACS & OLLE survey data at baseline)
	SAVFU			
	CHECKFU	1 = yes, 0 = no	Dichotomous	

Handling missing data

Outcomes

When creating the composite measures for co-parenting and parenting relationships, we will create a composite score by taking the average of multiple individual items. For these measures, our current plan is to use 20% as a threshold for allowable missing items, based on guidance from evaluation technical assistance resources. This plan is contingent on the final distribution of missing data in our data set. With a 20% threshold, if a respondent is missing more than 1 item used for creating the co-parenting construct or more than 2 items for creating the parenting construct, the respondent will be assigned a missing value for that construct. We will not be imputing truly missing values for outcomes. To create a construct score, the average will divide by the number of non-missing values in the construct.

Participants who have not seen their child within the past month will have their parenting behavior responses set to "Never" (1) and will be included in the analytic sample for that outcome.

For outcomes that use single survey items, participants who do not respond to the item on either the pre- or post-survey will be excluded from the analytic sample for that outcome.

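### R3 (financial behavior) is confirmatory and asks about a significant change, but the SAP only compares percentages for its yes/no items, with no test or interval

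*SAP*

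**What the plan says.** Protocol 1.1 lists R3 as a secondary outcome and asks: "Will participants report significantly healthier financial behavior one-year after completing primary educational services and employment support services". Protocol 1.2 then classifies it as confirmatory, which that table defines as an outcome that conclusions will rest on: participants "will report healthier financial behavior one year after AID! enrollment. Confirmatory".

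The power table in protocol 8.2 gives Father Financial Behavior (Outcome 3) a two-tailed test at 0.05, 80% power and an analytic sample of 483. It types all three outcomes the same way: "Continuous or binary? Continuous Continuous Continuous".

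The measure itself is not continuous. Protocol 9.1 describes it as "2 items: yes or no questions for have resume, checking/savings accounts (dichotomous"), and the SAP's model table types the financial items as dichotomous ("CHECKFU 1 = yes, 0 = no Dichotomous").

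In SAP section 1, Analytic approach, one sentence says: "We will use paired sample t-tests to assess the magnitude and significance of changes among program participants in the analytic sample for each outcome". The next deals with the binary items separately: "For binary economic stability outcomes, we will descriptively report the percent of participants who opened a checking or savings account one year after enrollment", compared with the percent before the program. The SAP goes on to promise p-values adjusted for multiple testing, but names neither the method nor the family of tests. It plans no confidence interval anywhere.

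**The concern.** Three parts of the protocol commit R3 to an inferential answer, while the SAP sentence written for its items offers only a description. Two percentages show the direction and size of the net change. They do not show whether it exceeds chance, because the precision of a paired difference depends on how many fathers switched each way, and the plan does not report switching.

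The general t-test sentence leaves a second route open. An analyst could test R3 or merely describe it, and could choose after seeing the result, for an outcome that conclusions are to rest on. The 80% power stated for Outcome 3 does not help, since it belongs to a continuous-outcome test that does not fit these items.

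**Working it through.** **Inputs from the documents.** Analytic sample 483, two-sided alpha 0.05, power 80% (protocol 8.2); expected one-year response 70% (protocol 9.5). The documents give no rate at which fathers gain or lose an account or resume, so the discordant share ψ is assumed at 10% to 40%. The 5-point net change is also illustrative.

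**The plan's own figure.** The power table gives a minimum detectable effect of 0.030. For a paired continuous outcome the detectable effect is (1.960 + 0.842)/√483 = 0.127 SD. An effect of 0.030 SD would need (2.802/0.030)² ≈ 8,721 pairs. So 0.030 does not follow from the stated inputs. The present point does not depend on that figure: the row matters here because it presupposes a significance test for R3.

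**Same percentages, different evidence.** With net change d = 0.05 and n = 483:

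- McNemar z = d·√(n/ψ)
- 95% CI = d ± 1.96·√((ψ − d²)/n)

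| ψ | z | two-sided p | 95% CI (points) |
|---|---|---|---|
| 10% | 3.475 | 0.0005 | 2.2 to 7.8 |
| 20% | 2.457 | 0.014 | 1.0 to 9.0 |
| 30% | 2.006 | 0.045 | 0.1 to 9.9 |
| 40% | 1.737 | 0.082 | −0.6 to 10.6 |

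All four rows could come from the same pair of reported percentages.

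If 483 is the number before one-year attrition, 0.70 × 483 ≈ 338 pairs remain, and p becomes 0.004, 0.040, 0.093 and 0.146.

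**What a binary power row would show.** The detectable d solves d·√n = z(1−α/2)·√ψ + 0.842·√(ψ − d²). At 80% power, in percentage points:

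| n, alpha | ψ = 10% | ψ = 20% | ψ = 30% |
|---|---|---|---|
| 483, 0.05 | 4.0 | 5.7 | 7.0 |
| 483, 0.0125 (0.05/4) | 4.8 | 6.8 | 8.3 |
| 483, 0.0071 (0.05/7) | 5.1 | 7.2 | 8.8 |
| 338, 0.05 | 4.8 | 6.8 | 8.3 |

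Both adjusted alphas are illustrative Bonferroni values, because the SAP names no method. Four is the number of research questions; seven is the number of dependent variables named in the SAP table.

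**The case against.** The strongest reply is that R3 is tested after all. The SAP calculates change scores for standalone survey items, its table lists the financial items as single items, and the next step is a paired t-test for each outcome with adjusted p-values. On that reading the percentages only supplement a test. A paired t-test on 0/1 items gives almost the same p as McNemar (0.0139 against 0.0140 at 20% discordance), so the choice between them is largely preference.

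This stands as a possible reading, and the point here is not McNemar against the t-test. But the sentence that singles out the binary items and calls their report descriptive reads more naturally as an exception. If it is not one, the two sentences still need reconciling.

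Other points stand in part:

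- R3 is secondary, the study has a single group and calls itself descriptive, and the 8.2 template makes power optional without an impact evaluation. That limits the weight of the point. It does not remove it, because the SAP tests change for the other outcomes and the plan itself chose the confirmatory label.
- The restriction to fathers with both answers is already in the SAP's missing-data rules, so that part of the fix needs no new rule.
- The SAP is dated October 17, 2024, and follow-up began 4/1/2022. Much outcome data may already exist, so the change should be dated and should say what has been seen.
- The mismatch in item lists rests partly on a table broken in extraction, although the SAP's prose on the binary outcomes also mentions only accounts.

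**Conclusion.** The concern holds and should be fixed. The plan labels R3 confirmatory and asks about significance, but does not clearly commit to any test or interval for its yes/no items. On the more natural reading there is none.

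The consequence is material at the planned size: one 5-point rise in 483 fathers can correspond to p anywhere from 0.0005 to 0.082, and the planned report cannot separate these cases. Those values rest on assumed discordance of 10% to 40% and on 483 being the number of complete pairs; with 338 pairs the evidence is weaker throughout. The conflict between the passages depends on none of these assumptions.

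**What to change.** In the SAP:

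- Replace the descriptive sentence with McNemar's test (exact if discordant pairs are few) for each R3 item, using the complete pairs the SAP already defines.
- Report the paired difference in proportions with a 95% confidence interval, and the number of fathers switching each way.
- Limit the t-test sentence to continuous outcomes.
- Include the R3 p-values in the promised adjustment, and name its method and family.

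In the protocol:

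- Use one R3 item list in section 9.1 and the SAP. Section 9.1 has a resume plus checking/savings accounts; the SAP table shows SAVFU and CHECKFU.
- Change the Outcome 3 power row to binary, and restate the detectable difference for a stated discordance, alpha and number of one-year pairs.

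If no test is wanted, relabel R3 exploratory, drop the significance wording and remove its power row.

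Make either change in a dated amendment stating which one-year data have been examined.

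The cost is a few lines and one extra test per item, with no new data collection. The multiplicity family grows: if every dependent variable in the SAP table is tested, it goes from five to seven, and a Bonferroni alpha falls from 0.05/5 = 0.010 to 0.05/7 = 0.0071, which costs the other outcomes some power. Relabelling adds no tests but gives up the confirmatory claim for R3.

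### The SAP promises multiplicity-adjusted p-values but gives them no role in the confirmatory conclusions, and the power table makes no allowance for the adjustment

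*SAP*

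**What the plan says.** - **Status of the questions.** Each question in Protocol 1.1 opens "Will participants report significantly". Protocol 1.2 labels all four confirmatory, meaning that conclusions will be drawn from them. Protocol 1.1 nevertheless calls R3 and R4 secondary.
- **Tests.** The SAP's model table lists seven dependent variables. Five are scaled or continuous: HOURSFU, REACHFU, ENGAGFU, COPARFU and PATTFU. Two are yes/no account items: SAVFU and CHECKFU. Under Analytic approach, paired t-tests are planned for each outcome, but the binary items are to be reported descriptively as percentages.
- **Multiplicity.** One sentence in the same section says p-values will be adjusted and that the team will "report the adjusted p-values in the appendix of the final report". The SAP gives no method, family, alpha or decision rule.
- **Power.** Protocol 8.2 sets a two-sided test and 80% power for three outcomes, with these rows: "Level of significance (e.g., 0.05 percent) 0.05 0.05 0.05", "Total number of individuals in analytic sample 483 483 483" and "Minimum detectable effect size 0.030 0.030 0.030". The standard deviation and covariate rows hold no numbers.

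**The concern.** An adjustment controls error only if the adjusted value decides the claim. Here a report could call an outcome significantly improved on an unadjusted p-value, print the adjusted one in an appendix, and comply fully with the SAP. The commitment also covers only the final report. SAP section 3 plans at least one manuscript and two professional presentations, and nothing requires adjusted values there.

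The family is open as well. The SAP allows weakly correlated items to be removed and drops an outcome whose reliability coefficient stays below 0.7. Its missing-data section refers to a parenting construct, while its model table lists three parenting variables. With no method or family named, both could be settled after results are known.

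The 80% power in 8.2 belongs to tests at 0.05. It does not carry over to tests at an adjusted level.

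**Working it through.** **Inputs.** From Protocol 8.2: N = 483, two-sided alpha 0.05, power 80%, minimum detectable effect 0.030 (metric not named). From the SAP: paired t-tests on at most five variables, or three if parenting behavior is one composite alongside co-parenting and parenting attitudes. Bonferroni is my assumption for the adjusted level, because the SAP names no method.

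**1. The plan's own figure.** For a paired t-test, the detectable standardised change is (z for 1 - alpha/2 + z for power)/√N.
- At 0.05: (1.960 + 0.842)/√483 = 2.802/21.98 = 0.127. The noncentral t gives 0.128. The stated 0.030 is not reproduced.
- Power at 0.030, read as a standardised mean change: 0.030 × 21.98 = 0.659, so power is Φ(0.659 - 1.960) + Φ(-0.659 - 1.960) = 0.097 + 0.004, about 10%.
- 80% power at 0.030 would need (2.802/0.030)², about 8,721 people.
- If 0.30 was meant, power exceeds 99.9% at 0.05 and still does at 0.01.
- A regression f² of 0.030 with seven predictors gives 79.8%. The documents state neither that metric nor a predictor count, and it is not the planned test.

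**2. Family-wise error if unadjusted p < 0.05 decides.** With k independent tests and every null true, it is 1 - 0.95^k. The correlated columns come from simulating equicorrelated normal test statistics.

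| Tests | Independent | Correlation 0.5 | Correlation 0.7 |
|---|---|---|---|
| 3 (R1 as one composite) | 1 - 0.857 = 14.3% | 12.6% | 10.9% |
| 5 (all planned t-tests) | 1 - 0.774 = 22.6% | 18.2% | 14.9% |

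**3. Power at the adjusted level, N = 483.** By normal approximation, power at the unadjusted detectable change is Φ(2.802 - z for 1 - alpha/2).
- Three tests, alpha 0.05/3 = 0.0167: Φ(2.802 - 2.394) = Φ(0.408), about 66%. The detectable change at 80% power is 0.148 SD (noncentral t).
- Five tests, alpha 0.05/5 = 0.01: Φ(2.802 - 2.576) = Φ(0.226), about 59%. The detectable change is 0.156 SD (noncentral t).

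Holm's first step equals Bonferroni and its later steps are less strict, so under Holm these powers are lower bounds for each test.

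**The case against.** The strongest reply is that the SAP does commit to adjustment and will disclose the results, so appendix or main table is a matter of presentation. The study is a single-group descriptive evaluation. The template asks for Type I error methods and for power only where an impact analysis is proposed, so the sponsor offered both voluntarily. This lowers the stakes. It does not remove the gap: the sponsor chose significance tests and confirmatory labels, and Protocol section 5 describes the comparisons as estimating the impact of participation.

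A reader might infer that the headline tests definitely use an unadjusted 0.05. The documents do not say so. The SAP states no threshold and leaves the decision rule open, so the error rates above are conditional.

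A reader might also put the family-wise error at 23-30%. The upper end, 1 - 0.95^7 = 30.2%, needs tests of SAVFU and CHECKFU, which the SAP only describes. The lower end is really the maximum for the planned t-tests, reached only with all five independent and every null true.

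The family is also disputable, because Protocol 1.1 calls R3 and R4 secondary. A family of primary outcomes only would have four t-tests (1 - 0.95^4 = 18.5%), or two with a composite (9.8%).

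Finally, 0.128 SD is this review's figure, not the plan's. The 80% is unsupported as a paired-test claim at 0.030 even before adjustment, so multiplicity is not the only fault in the power table, nor the larger one.

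**Conclusion.** The point holds in a conditional form. The adjusted p-values have no stated role in the confirmatory conclusions, and the plan permits unadjusted p < 0.05 to drive them. In that case the chance of at least one false claim is at most 22.6%, and about 11-18% with test-statistic correlations of 0.5 to 0.7, against a nominal 5%. These figures assume all nulls true and three to five paired t-tests.

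Separately, the 80% in 8.2 does not apply to adjusted tests. Under Bonferroni the loss is from 80% to between 66% and 59% at 0.128 SD. That loss would matter little if the intended effect was 0.30, which is a further reason for 8.2 to state its metric. This is more than missing detail, because it decides whether the promised error control operates. It is a correction the sponsor should make, not a flaw that undermines the study.

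**What to change.** - In the SAP, state that confirmatory conclusions rest on Holm-adjusted p-values over a listed family: HOURSFU, REACHFU, ENGAGFU and COPARFU, plus parenting attitudes (PATTFU). Add the R3 account items only if they are to be tested. If parenting behavior is to be one composite, say so and list that instead. Reconcile the secondary and confirmatory labels for R3 and R4 at the same time.
- Show adjusted values beside the unadjusted ones in the main results table, and apply the same rule to the manuscript and presentations.
- In Protocol 8.2, restate the minimum detectable effect, with its metric, for the paired t-test at the adjusted level. Under Bonferroni with 483 participants this is 0.148 SD for three tests or 0.156 SD for five.

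The cost is a few sentences, one table column, a somewhat stricter threshold and a less favourable stated detectable effect. No new data are needed.
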